9.4.1.2 Control of Experiment-wise Type I Error

Each of the co-primary endpoints will be tested by fitting a MMRM analysis at a two-sided significance level of 0.05 on OC dataset on Efficacy Sample, and the trial will be claimed positive if both p-values are less than 0.05. Therefore, the overall type I error is controlled at 0.05 level.

9.4.1.3 Other Efficacy Endpoint Analysis

The other efficacy endpoints are as follows. All of them will be evaluated at a nominal 0.05 level (2-sided) without adjusting for multiplicity on Efficacy Sample:

- 1) Change from baseline to Weeks 2 and 4 in IDS-SR-10-engagement.
- 2) Change from baseline to Weeks 2 and 4 in IDS-SR Total score.
- 3) Change from baseline to Weeks 2, 4, and 8 in IDS-SR patient-selected engagement items.
- 4) Change from baseline to Weeks 2, 4, and 8 in IDS-SR engagement items selected by both clinicians and patients.
- 5) Change from baseline to Weeks 2, 4, and 8 in CGI-S score.
- 6) CGI-I score at Weeks 2, 4, and 8.
- 7) Change from baseline to Weeks 4 and 8 in SDS Mean score and SDS individual item scores.
- 8) Change from baseline to Weeks 4 and 8 in WHODAS 2.0 short form score.
- 9) Change from baseline to Weeks 2, 4, and 8 in PHQ-9 score.
- 10) Change from baseline to Weeks 2, 4, and 8 in GAD-7 score.
- 11) Change from baseline to each timepoint (ie, being measured weekly at home) in depression as measured by PGI-I score.

- 12) PGI-I response rate at each timepoint (ie, being measured weekly at home), where response is defined as a PGI-I score of 1 or 2 (very much improved or much improved).
- 13) Time to first PGI-S response, where response is defined as a reduction of 2 points in PGI-S score from baseline.

Endpoint (1) - (5), (7) - (11) will be analyzed by fitting the same MMRM model described in the primary analysis on OC dataset. Endpoint (6) will be analyzed using one-sample t-test on LOCF dataset. Endpoint (12) will be evaluated using descriptive statistics on LOCF dataset. Endpoint (13) will be evaluated by time-to-event analysis with Kaplan-Meier curve on OC dataset.

9.4.2 Analysis of Demographic and Baseline Characteristics

Demographic and baseline characteristics (including age, weight, BMI, sex, race, and ethnicity) for Enrolled Sample will be summarized using descriptive statistics (frequency,

mean, median, standard deviation (SD), maximum, minimum, and percentage when applicable).

9.4.3 Safety Analysis

Safety analysis will be performed on the Safety Sample. Safety variables of interest mainly include AEs, body weight, BMI, and vital signs.

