1.3 Schedule of Assessments

			Visit		
Assessment	Screening ^a	Baseline ^a (Day -1)	Week 2	Week 4	Week 8 /ET ^b
	(Days -14 to -2)	± 5 days			
ENTRANCE/HISTORY					
Informed consent	X				
Inclusion/exclusion criteria	X	X			
Demography	X				
Medical history	X				
Psychiatric history	X				
Prohibited medication washout ^c	X				
Urine pregnancy test	X	X			
EFFICACY ^d					
IDS-SR (patient reported)		X	X	X	X
PHQ-9 (patient reported) ^e	X	X	X	X	X
GAD-7 (patient reported)		X	X	X	X
WHODAS 2.0 short (patient reported)		X		X	X
SDS (patient reported)		X		X	X
CGI-S		X	X	X	X
CGI-I			X	X	X
SAFETY					
Brief physical examination ^f	X				X
Height and body weight ^g	X	X	X	X	X
Vital signs ^h	X	X		X	X
Adverse events	X	X	X	X	X
Concomitant medications ⁱ	X	X	X	X	X

Table 1.3-1 Schedule of Assessments						
	Visit					
Assessment	G	Baseline ^a (Day -1)	Week 2	Week 4	Week 8 /ET ^b	
	Screening ^a (Days -14 to -2)	\pm 5 days				
Clinical evaluation for suicidality ^e	X	X	X	X	X	
OTHER						
Trial drug prescribed ^j		X	X	X		
Trial drug accountability (patient reported)			X	X	X	
Review of Patient Diary (word of the day, PGI-S, and PGI-I) ^k		X	X	X	X	

ADT = antidepressant therapy; CGI-I = Clinical Global Impression - Improvement; CGI-S = Clinical Global Impression - Severity; ET = early termination; GAD-7 = Generalized Anxiety Disorder 7-item scale; ICF = informed consent form; IDS-SR = Inventory of Depressive Symptomatology Self-Report; PGI-I = Patient Global Impression - Improvement; PGI-S = Patient Global Impression - Severity; PHQ-9 = Patient Health Questionnaire 9-item scale; SDS = Sheehan Disability Scale; WHODAS = World Health Organization Disability Assessment Schedule.

^aBrexpiprazole dosing will take place on Day 1 of Week 1. The screening visit can comprise 1 or more visits as needed. Screening and baseline visits can occur the same day if the patient meets all required enrollment criteria. Where screening and baseline visits occur on the same day, assessments will not be duplicated.

^bIf a patient discontinues prematurely before Week 8, every effort should be made to complete the "Week 8/ET" evaluations.

^cWashout of prohibited medications begins after signing the ICF and must comply with the required washout periods.

^dWhere possible, sites should follow the order of efficacy assessments and patient reported outcomes as listed.

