^eIf the PHQ-9 indicates suicidal ideation (eg, a patient has suicidality on item 9 of the PHQ-9 scale [≥ 1] and/or IDS item 18 ≥ 3), then clinical evaluation of suicidality is essential on that particular visit and the investigator will conduct a more in-depth clinical assessment of the patient per the site's standard protocol.

^fThe extent of the physical examination will be at the discretion of the investigator.

^gHeight and body weight at screening and body weight at baseline and at Weeks 2, 4, and 8/ET. When screening and baseline visits occur on the same day, assessments will not be duplicated.

^hVital signs include systolic and diastolic blood pressure and heart rate.

ⁱAll medications taken within 30 days prior to informed consent will be recorded. In addition, all prescription and non-prescription medications taken during the trial will be recorded as concomitant medications. All ADTs taken within 12 months prior to informed consent will be recorded.

^jTrial drug will not be prescribed at the Week 8 visit. The ADT regimen will be left to the discretion of the investigator.

^kPatient diary entries will be reduced in frequency from daily to twice weekly from Week 5 to Week 8 (word of the day and PGI-S). The PGI-I will be administered weekly throughout the trial.

2 Introduction

Major depressive disorder (MDD) is a serious medical illness associated with significant suicide risk and marked disability. Symptoms are heterogenous, spanning emotional, physical and cognitive domains, and lead to impairments in personal and social functioning, as well as diminished quality of life. Importantly, patients want a treatment that will help them to regain optimism and self-confidence, feel like their usual selves, and regain their pre-morbid level of functioning and feelings of well-being. The return to premorbid levels of functioning are often rated by patients as more important than symptom relief. Given that full symptomatic and functional recovery is the goal of MDD treatment, early identification of treatments that can address a broad range of symptoms of the illness are needed in order to effectively treat the consequences on overall functioning and well-being, and help the patient return to their premorbid state.

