8.2.3 Suicidality Monitoring

A suicidality assessment will be conducted using the PHQ-9 suicidality item and/or as per the trial site's standard operating procedures (SOPs). If the PHQ-9 indicates suicidal ideation (eg, a patient has suicidality on item 9 of the PHQ-9 scale [\geq 1] and/or IDS item $18 \geq 3$), then clinical evaluation of suicidality is essential on that particular visit and the investigator will conduct a more in-depth clinical assessment of the patient per the site's SOPs.

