8.3.2 Eliciting and Reporting Adverse Events

The investigator will regularly assess patients for the occurrence of AEs. To avoid bias in eliciting AEs, patients should be asked the nonleading question: "How have you felt since your last visit?" All AEs (serious and nonserious) reported by the patient must be recorded on the source documents and CRF provided by the sponsor. Adverse event collection will begin after a patient signs the ICF, and will continue until the Week 8/ET visit. All AEs must be reported after patient informed consent has been obtained, including screening failures due to AEs, irrespective of trial drug administration.

Medical terminology should be used for AE reporting. Adverse events should be reported as a single unifying diagnosis whenever possible or, in the absence of a unifying diagnosis, as individual signs or symptoms.

Exacerbation or disease progression should be reported as an AE only if there are unusual or severe clinical features that were not present, or experienced earlier, or not expected based on the course of the condition.

In addition, the sponsor must be notified immediately by telephone, fax, or e-mail of any IREs according to the procedure outlined below, in Section 8.3.3. Special attention should be paid to recording hospitalization and concomitant medications.

The adverse event, start date and time, end date and time, seriousness, severity, relationship to trial treatment (trial drug causality), action taken with trial treatment, and outcome will be recorded on the source documents and in the CRF.

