### 6.2 Safety Variables

The safety of the open-label brexpiprazole is assessed based on reported adverse events (AEs), vital signs, body weight, BMI, and physical examination,

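### Suicidality is assessed for safety at every visit but is named in no safety analysis, so non-serious ideation judged expected can be missing from the safety results

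*Protocol*

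**What the plan says.** **Assessment.** Protocol Section 8.2.3 sits under the safety assessments and reads: "A suicidality assessment will be conducted using the PHQ-9 suicidality item and/or as per the trial site's standard operating procedures". If PHQ-9 item 9 is 1 or more, and/or IDS item 18 is 3 or more, "then clinical evaluation of suicidality is essential on that particular visit". The safety block of Table 1.3-1 has a row for this, "Clinical evaluation for suicidality", marked at screening, baseline and Weeks 2, 4 and 8/ET.

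**Analysis.** Protocol Section 9.4.3 states: "Safety variables of interest mainly include AEs, body weight, BMI, and vital signs". In SAP Section 6.2, safety "is assessed based on reported adverse events (AEs), vital signs, body weight, BMI, and physical examination". SAP Section 9 names the same variables. The synopsis lists of safety assessments and safety endpoints do not mention suicidality either.

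**AE reporting.** Protocol Section 8.3.2: "Exacerbation or disease progression should be reported as an AE only if there are unusual or severe clinical features". The sentence goes on to require that these features be new or not expected from the course of the illness.

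**The concern.** Safety and tolerability is a secondary objective, and the Introduction (Protocol Section 2) describes MDD as a "serious medical illness associated with significant suicide risk and marked disability". The trial collects two suicidality items repeatedly, yet no stated safety variable uses them. The AE tables are the only other route into the safety results, and the reporting rule filters out worsening that is regarded as part of the illness. A report that follows the plan exactly could therefore say nothing about ideation that emerged or worsened during treatment, even where the trial's own item scores show it. The trial has no control arm and no data monitoring committee, so the final report is where a pattern across patients would be seen.

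**Working it through.** The documents give no figure for suicidality to reproduce, and the sample-size figures do not bear on the point. The check is a comparison of sections, with a little arithmetic.

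**1. Safety-block rows of Table 1.3-1 against visible outputs**

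| Row | Visible output |
|---|---|
| Physical examination | Listing (Protocol 9.4.3.2, SAP 9.5) |
| Height and weight | Summaries and incidence tables for weight, summaries for BMI (Protocol 9.4.3.2, SAP 9.4) |
| Vital signs | Summaries and incidence tables (Protocol 9.4.3.2, SAP 9.4) |
| Adverse events | Tables and listings (Protocol 9.4.3.1, SAP 9.2) |
| Concomitant medications | Tabulation and listing (SAP 7.5) |
| Suicidality evaluation | None visible |

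Pregnancy tests, which are outside the safety block, also have a listing (SAP 9.3).

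**2. Can the AE tables miss it?**
- Entry requires PHQ-9 of at least 15. IDS-SR item 18 = 3, or serious risk in the investigator's opinion, excludes a patient. Item 18 scores of 0 to 2 do not exclude by score. Some ideation can therefore be present at baseline, and an investigator could regard more of it as part of the episode.
- Suppose PHQ-9 item 9 goes from 0 to 1. The Section 8.2.3 trigger is met and the evaluation takes place. Nothing in either document says that a positive screen or evaluation must be recorded as an AE. Under Section 8.3.2, no AE is due if the change is judged expected and not severe.
- Suppose instead that item 18 goes from 0 to 1 or 2. This does not reach the item 18 trigger of 3, and the same AE rule applies.
- The TEAE definition does cover events that continue from baseline and worsen, but it works only on events already recorded as AEs.

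**3. Would the efficacy analyses show it?**
- IDS-SR Total: 28 items × 3 = 84 points. Item 18 contributes at most 3/84 = 3.6%.
- PHQ-9: 9 items × 3 = 27 points. Item 9 contributes at most 3/27 = 11.1%.
- Item 18 is in neither the clinician-selected nor the patient-selected engagement score (SAP 11.2.2 and 11.2.3).
- The totals are analysed as mean change in the Efficacy Sample. That sample omits dosed patients without a post-baseline IDS-SR evaluation, and the SAP visit windows drop evaluations made more than seven days after the last dose. One patient's worsening on one item cannot be read from these results.

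**4. What the item data could support.** Suppose all 134 enrolled patients were dosed and assessed after baseline, and none had a given outcome. The exact two-sided 95% upper limit would be 1 − 0.025^(1/134) = 2.7%. Fewer assessed patients would raise the limit. This illustrates the use of the data and does not measure the gap.

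**The case against.** Several counter-arguments have weight.

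- **Unseen pages.** SAP Section 8.3 and Appendix 2 are not in the text reviewed, so a suicidality table may be listed there. This stands, and it limits the point to what is visible. Even then, SAP Sections 6.2 and 9 would still need to name the variable, population and definitions.
- **Internal consistency.** The synopsis does not declare suicidality a safety endpoint, and the analysis sections largely follow the synopsis. Section 8.2.3 can be read as monitoring to protect the individual patient. This also stands: no declared safety endpoint is left unanalysed. It does not explain why this is the only safety-block row without a visible output.
- **An open list.** The word mainly in Protocol Section 9.4.3 allows other variables. However, SAP Sections 6.2 and 9 do not add this one.
- **The AE rule.** No passage classes suicidal ideation as expected worsening, and the AE definition is broad. That is right: the gap depends on an investigator's judgement, which the rule permits but does not require.
- **Source of risk.** The Introduction's remark concerns the disease, not the drug. This is fair, but suicidality is still the trial's own safety assessment.

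A reader might infer that emergent suicidality will be missing altogether, even a rise from 0 to 3 on item 18. The documents do not support that. A new top score meets the Section 8.2.3 trigger and is the kind of new, severe feature that Section 8.3.2 admits as an AE. Deaths, serious events and discontinuations due to AEs have their own tables and listings.

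**Conclusion.** The point holds in a limited form. In the visible text, suicidality is assessed at every visit but is named in no safety analysis. The AE rule allows emergent or worsening ideation to go unreported when it is non-serious and judged expected. Such cases can be absent from the safety results; it does not follow that they will be.

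The number of patients affected cannot be estimated, because the documents give neither a rate of ideation nor any guide to how investigators would apply the rule. The conclusion assumes that the unseen SAP Section 8.3 and Appendix 2 contain no such output, and that some investigators would regard milder ideation as part of the depressive episode. It implies no defect in the monitoring of individual patients. What is missing is a summary across patients, and it bears directly on the safety objective.

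**What to change.** Name suicidality as a descriptive safety variable in Protocol Section 9.4.3 and SAP Section 6.2, and add a subsection to SAP Section 9, on the Safety Sample:

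1. Distribution of PHQ-9 item 9 and IDS-SR item 18 at baseline and each visit.
2. Shift from baseline to worst post-baseline value, using scheduled and ET values, and unscheduled values where collected.
3. Number and percentage with any worsening, and with emergence (for example, 0 at baseline and at least 1 later), with the number assessed as denominator.
4. A listing of patients who meet the Section 8.2.3 trigger, with any related AE.

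The emergence cut-off and the worst-value rule are analysis choices that the documents do not supply, so they should be fixed before the data are analysed. The trigger also needs one definition for the listing: the footnote to the continuity-plan schedule (Table 10.5.1.2-1) mentions only PHQ-9 item 9, whereas Section 8.2.3 also mentions IDS item 18. Those passages must be reconciled. If Appendix 2 already lists such outputs, only the text of the sections needs to be aligned.

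The cost is some protocol and SAP wording and a few outputs from data already collected. Assessments, sample size and patient care do not change. With a single arm, the results can only be descriptive and cannot attribute any change to the drug.

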9.4.3.1 Adverse Events

All AEs will be coded by system organ class and Medical Dictionary for Regulatory Activities preferred term. The incidence of the following events will be summarized by descriptive statistics:

- TEAEs
- TEAEs by severity
- TEAEs potentially causally related to the trial drug
- TEAEs with an outcome of death
- Serious TEAEs
- TEAEs leading to discontinuation of the trial drug

Adverse event data will also be presented in listings.

9.4.3.2 Physical Examination and Vital Signs Data

Physical examination data will be presented in a listing.

Descriptive statistics will be used to summarize body weight and BMI at screening, baseline, and Weeks 2, 4, and 8/ET. The incidence of potentially clinically significant changes in body weight will be tabulated in incidence tables.

Descriptive statistics for changes from baseline in vital signs will also be provided. Potentially clinically significant results in vital signs will be summarized.

10 Supporting Documentation and Operational Considerations

10.1 Appendix 1: Regulatory, Ethical, and Trial Oversight Considerations

10.1.1 Ethics and Responsibility

This trial must be conducted in compliance with the protocol, applicable ICH GCP guidance, international ethical principles derived from the Declaration of Helsinki and Council for International Organizations of Medical Science (CIOMS) guidelines, and applicable local laws and regulations. Each trial site will seek approval/favorable opinion by an IRB or IEC according to regional requirements, and the investigator will provide that documentation to the sponsor. The IRB/IEC will evaluate the ethical, scientific, and medical appropriateness of the trial. Further, in preparing and handling the CRF, IRE and any safety information, the investigator, subinvestigator, and their staff will take measures to ensure adequate care in protecting patient privacy. To this end, a patient ID will be used to identify each patient.

Financial aspects, patient insurance, and the publication policy for the trial will be documented in the agreement between the sponsor and the investigator.

10.1.2 Informed Consent

Informed consent will be freely obtained from all patients (or legally acceptable representative, as applicable for local laws). The ICF will be approved by the same IRB/IEC that approves this protocol.

Each ICF will comply with the International Council for Harmonisation (ICH) GCP Guidelines, and local regulatory requirements. The investigator will ensure that the sponsor reviews and authorizes any site-specific ICF used in the trial before submission to the IRB/IEC. Trial sites will have patients review and sign the ICF prior to starting any trial procedures.

Investigators may discuss trial availability and the possibility for entry with a potential patient without first obtaining consent. However, informed consent must be obtained and documented before initiation of any procedures that are performed solely for the purpose of determining eligibility for this trial, including withdrawal from current medication(s).

Potential patients are free to refuse entry into the trial, or withdraw from the trial at any time, without justification, and there will be no consequences to their further care.

Prospective trial patients will be provided with study protocol information by the trial site staff. When the trial site staff and the patient agree that the patient has enough

information to make an informed decision to participate, the patient will sign the ICF. The patient will be given a printed, signed copy of the ICF. Any other parties required by the IRB/IEC (trial site staff, witnesses, or legally authorized representative) are also required to sign the ICF in accordance with the ICH GCP Guideline and local regulatory requirements/guidelines. These signatures cannot be altered, removed, or copied.

Once appropriate essential information has been provided and fully explained in layman's language to the patient by the investigator (or a qualified designee), and it has been documented that the patient has had the opportunity to ask questions, the IRB/IEC-approved ICF will be signed and dated by both the patient and the person obtaining consent (investigator or designee), as well as by any other parties required by the IRB/IEC. The patient will receive a copy of the signed ICF; the original shall be kept on file by the investigator.

Patients may be asked to sign additional ICFs if the protocol is amended and the changes to the protocol result in additional information that needs to be provided to the patients, so that they can make a knowledgeable and voluntary decision on continued trial participation. Female partners of male patients who become pregnant during the course of the trial may be asked to sign additional ICFs in order to collect additional information regarding the nonpatient partner and fetus.

10.1.3 Confidentiality

All information generated in this trial will be considered confidential and will not be disclosed to anyone not directly concerned with the trial without the sponsor's prior written permission. Patient confidentiality requirements of Canada where the trial is conducted will be met. However, authorized regulatory officials and sponsor personnel (or their representatives) may be allowed full access to inspect and copy the records, consistent with local requirements. All IMPs and/or other materials collected shall be used solely in accordance with this protocol, unless otherwise agreed to in writing by the sponsor.

Patients will be identified only by unique patient ID in the CRF. If further patient identification is required, patients' full names may be made known to a regulatory agency or other authorized officials if necessary, patient to local regulations.

